## **Full description**

### **Introduction**

Embryo aneuploidy is likely the leading cause of implantation failure in IVF cycles. Since the inception of IVF, non-invasive morphology based scoring has been the most widely used embryo selection method, resulting in relatively low embryo implantation rates. Embryo morphology assessment methods have significant limitations (i.e., the assessments are subjective and the method uses fixed time-point assessments to define dynamic embryo development) and shortcomings (i.e., exposes embryos to sub-optimal conditions during assessment). Notwithstanding the limitations and shortcomings of this method its use worldwide has continued, because it is a relatively simple and non-invasive method and its scores have been shown to be (moderately) positively correlated to embryo euploidy, ongoing pregnancy, and live birth (Van Royen *et al.*, 1999, Ahlstrom *et al.*, 2011, Forman *et al.*, 2013, Capalbo *et al.*, 2014, Oron *et al.*, 2014, Rhenman *et al.*, 2015).

However multiple gestations still represents one of the most significant complications in IVF, which are mainly the result of multiple-embryo embryo transfers, with multiple-embryo transfers used to overcome the relatively low embryo implantation rates in IVF. Our understanding of the optimal conditions required for *in vitro* embryo culture in IVF has advanced significantly in the past two decades. The implementation of improved *in vitro* embryo culture technologies (i.e., culture media and incubators) has resulted in an increase in the number of good quality embryos and consequently in the numbers of blastocysts. While blastocyst transfers have seemingly improved the reproductive outcomes in IVF, the use of SET and PGT technologies have revealed embryo implantation still to be sub-optimal (Schoolcraft *et al.*, 2013). New CCS platforms are a major breakthrough in PGT, allowing 24-chromosome screening to be performed with high degree of accuracy from single cells (Harper and Harton, 2010). The evidence that morphology scores were only moderately associated with euploidy and that the transfer of PGT predicted euploid embryos resulted in higher implantation rates (Dahdouh *et al.*, 2015), has seen the continued use of morphology based scoring methods increasingly being challenged.

In addition to all the other advances in IVF, significant improvements have also been made in cryopreservation technologies. These improvements have resulted in significant improvements in frozen-thawed embryo survival (i.e. minimizing of risks), post-thaw developmental competence (Cobo *et al.*, 2012; Balaban *et al.*, 2008), and in the reproductive outcomes of FET (Evans *et al.*, 2014; Ozgur *et al.*, 2015). The benefits of FET include; the transfer of embryos to a more physiologic endometrium (i.e., early luteal phase), the ability to time transfers more accurately, and

the ability to use patient specific endometrial preparations (Casper and Yanushpolsky, 2016, Franasiak *et al.*, 2016; Groenewoud *et al.*, 2013, Yarali *et al.*, 2016).

Moreover, the hypotheses of PGT require to be confirmed in further robust RCT before its implementation in routine IVF.

## Objectives

The primary objective of this RCT will be to investigate whether PGT for aneuploidy as a blastocyst selection method is superior to standard morphology scoring blastocyst selection, comparing the reproductive outcomes in FET cycles. The decision to transfer all blastocysts in FET will eliminate any potential impact of ovarian stimulation confounding on endometrial receptivity and to use freeze-all cycles will allow the use of the primary blastocysts of blastocyst cohorts. The primary outcome measure of this trial will be LB, with a LB defined as a pregnancy cycle delivering at >20 weeks of gestation.

## Secondary objectives

The secondary objective of the RCT will be to investigate whether euploid blastocyst transfer results in reduced miscarriage, with a miscarriage defined as a clinical pregnancy lost at <20 weeks of gestation.

**Keywords:** blastocyst; comprehensive chromosome screening; euploidy; frozen embryo transfer

**Funding:** This RCT will not receive any specific grant from funding agencies in the public, commercial, or not-for-profit sectors, and therefore will be wholly funded by centre running the trial.

**Declaration of Interests:** The authors declare no conflicts of interest.

## **Materials and methods**

### **Study design**

The RCT will be performed as a single private IVF center trial. The patient population of the trial will include young patients undergoing autologous blastocyst freeze-all IVF cycles from March 2017. In this trial, a patient will undergo a blastocyst-freeze-all cycle after ICSI and only the reproductive outcomes of the first FET following the freeze-all will be analyzed. Currently at the trial centre more than 95% of cycles are extended culture cycles and more than 80% of these cycles result in freeze-all cycles, with a live birth rate after the first FET of >45% per oocyte retrieval.

## **Study population/Participants and recruitment**

The trial participants will consist of infertile patient-couples attending Antalya IVF for autologous segmented-IVF treatment. Patients will be informed of the trial at their clinical consultation before commencing treatment, at which the trial procedures and the likely reproductive outcomes will be discussed. All patients who consent to participation and who satisfy the inclusion criteria will undergo the same standard IVF procedures; ovarian stimulation (OS), oocyte retrieval, ICSI, extended embryo culture, blastocyst vitrification, and artificial FET.

## **Eligibility criteria**

Patient-couples eligible for inclusion in the trial must satisfy the following criteria; female age of  $\leq 35$  years, female body mass index (BMI) of  $\geq 18$  or  $\leq 35$  kg/m^2, antral follicle count (AFC) of  $\geq 5$  (changed from  $\geq 10$ ), normo-ovulatory, intend to use autologous oocytes, and have  $\geq 2$  blastocysts with a morphological score of 2BB on day 5 of embryo development.

## **Exclusion criteria**

Patient couples will be excluded from the trial for the following reasons, patients with drug contraindications, patients with pathophysiology unrelated to reproduction, patients with intrauterine pathophysiologies, patients with no blastocysts, patients with  $<2$  blastocysts with a morphological score of 2BB.

## **Randomisation**

Patient couples who satisfy the inclusion criteria and who completed an informed consent will randomized by computer generated number in a 1:1 ratio on day 5 of in vitro embryo culture to the two arms, with the FET drug prescription indicating allocation to the ***the PGT group***, in which all blastocysts will be assessed according to standard morphological parameters, with the best scoring blastocyst to undergo biopsy and PGT for aneuploidy or ***the morphology group***, in which all blastocysts will be assessed according to standard morphological parameters, with the best scoring blastocyst selected for transfer (figure 1). Patient couples in the PGT group will be subgrouped

according to whether the blastocyst biopsied is predicted to be euploid (**the euploid subgroup**) or aneuploid (**the aneuploid subgroup**). In the aneuploid group the next best morphology scoring blastocyst will be transferred.

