## **Description**

### **Brief description**

#### Introduction

Embryo aneuploidy is likely the leading cause of implantation failure in IVF cycles. Since the inception of IVF, non-invasive morphology based scoring has been the most widely used embryo selection method, resulting in relatively low embryo implantation rates. Our understanding of the optimal conditions required for *in vitro* embryo culture in IVF has advanced significantly over the past two decades. The implementation of improved *in vitro* embryo culture technologies (i.e., culture media and incubators) has resulted in an increase in the number of good quality embryos and consequently in increased numbers of blastocysts. While blastocyst transfers have seemingly improved the reproductive outcomes of IVF, they still remain suboptimal. The main objective of this randomized controlled trial (RCT) will be to investigate whether preimplantation genetic testing (i.e., PGT with comprehensive chromosome screening (CCS)) for aneuploidy is a superior embryo selection method, with the live birth outcomes of euploid blastocyst frozen embryo transfers (FET) compared with the LB outcomes of unknown-ploidy blastocyst FET, with blastocysts selected on (standard) morphological score.

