### *Sample size calculation*

At the trial centre the overall ongoing pregnancy rate was 66% for the transfer CCS euploid blastocysts, while the overall ongoing pregnancy rate was 52% for blastocysts selected for transfer by morphology only. The sample sizes required to have 80% chance of detecting a difference of 20% at a significance level of 0.05 was calculated to be 74.

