## **Data**

All data pertaining to the trial and required for analysis will be collected by the principal investigator from the IVF database of Antalya IVF at >20 weeks after the last patient randomized had

undergone FET. A LB cycle will defined as a pregnancy cycle delivered at >20 weeks of gestation. A clinical pregnancy will defined as a pregnancy cycle with a fetal sac observed on ultrasound at >5 weeks of gestation. A miscarriage will be defined as a clinical pregnancy lost at <20 weeks of gestation.

**Figure 1:** Study design

Eligible patients		Enrollment	Inclusion criteria:
			Own oocytes; normo-ovulatory; $\leq 35$ years of age; $\leq 3$ embryo transfers; $\geq 18$ - $\leq 35$ kg/m  BMI; $\geq 5$ AFC. Informed consent
Assessment:		Randomization	Exclusion:
			No oocytes retrieved; $< 2$ blastocysts with morphological grade of $\geq 2$ BB
Assessment:			
			All blastocysts assessed morphologically
PGT group  1 blastocysts with morphological grade of $\geq 2$ BB biopsied and assessed by NGS	All blastocysts with morphological grade of $\geq 2$ BB cryopreserved	Morphology group	All blastocysts with morphological grade of $\geq 2$ BB cryopreserved
aneuploid blastocyst	euploid blastocyst		
Aneuploid subgroup: transfer of morphologically assessed blastocyst  Positive $\beta$ hCG 9 days of transfer	Euploid subgroup: transfer of a euploid blastocyst  Positive $\beta$ hCG 9 days of transfer	Morphology group: transfer of a morphologically assessed blastocyst  Positive $\beta$ hCG 9 days of transfer	

Fetal sac on ultrasound >5 weeks	Fetal sac on ultrasound >5 weeks	Secondary outcome measure	Fetal sac on ultrasound >5 weeks
--	--	----------------------------------	--

Live birth: Delivery at >20 weeks	Live birth: Delivery at >20 weeks	Primary outcome measure	Live birth: Delivery at >20 weeks
---	---	--------------------------------	---

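### The sample size rests on euploid-transfer rates, makes no allowance for PGT-group patients who receive an untested blastocyst, and does not say which comparison the 74 serves

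*Combined protocol and SAP*

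**What the plan says.** All places are in the combined protocol and SAP.

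- **Randomisation.** Couples are allocated 1:1 on day 5, before any PGT result exists. In the PGT group all blastocysts are graded, "with the best scoring blastocyst to undergo biopsy and PGT for aneuploidy". If that one is aneuploid, the patient stays in the PGT group as part of an aneuploid subgroup: "In the aneuploid group the next best morphology scoring blastocyst will be transferred".
- **Figure 1 (under Data).** One blastocyst is biopsied per PGT-group patient. The aneuploid subgroup's box reads "transfer of morphologically assessed blastocyst".
- **Sample size calculation.** The inputs are "the overall ongoing pregnancy rate was 66% for the transfer CCS euploid blastocysts" and "the overall ongoing pregnancy rate was 52% for blastocysts selected for transfer by morphology only". The result is an "80% chance of detecting a difference of 20% at a significance level of 0.05 was calculated to be 74".
- **Introduction (Brief description).** The aim is to learn whether PGT is the better selection method, which is then described as "live birth outcomes of euploid blastocyst frozen embryo transfers (FET) compared with the LB outcomes of unknown-ploidy blastocyst FET".
- **Objectives.** The question is whether "PGT for aneuploidy as a blastocyst selection method is superior to standard morphology scoring blastocyst selection".
- **Secondary objectives.** Miscarriage is framed as an effect of euploid transfer.
- **Statistics.** The chi-square or Fisher's exact test is named, with p < 0.05. No primary comparison, analysis set or sidedness is given.

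**The concern.** The two rates behind the sample size describe types of transfer, whereas the trial randomises strategies. Some PGT-group patients will have an aneuploid result and receive a blastocyst of unknown ploidy, as every morphology-group patient does. Those patients pull the PGT-group rate towards the morphology rate, so the difference between randomised groups is smaller than the euploid-transfer effect. The calculation contains no euploid fraction, no blended rate and no inflation.

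The plan also leaves open which contrast the 74 is meant to power. PGT group v morphology group is randomised but diluted. Euploid subgroup v morphology group is undiluted, but it drops patients from one arm only, on a result obtained after randomisation, so it no longer compares randomised groups.

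Two misreadings follow. A non-significant result for the randomised groups could be taken as evidence about euploid transfer, when it concerns a diluted strategy. A favourable euploid-subgroup result could be taken as randomised evidence.

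**Working it through.** **Inputs from the plan.** Euploid rate 66%, morphology rate 52%, difference 20 points, power 80%, significance level 0.05, stated size 74.

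**Assumptions not in the plan.** 74 is per arm. Ongoing pregnancy rates stand in for live birth. Biopsy itself has no effect. Untested next-best blastocysts succeed at 52%. The fraction *e* of PGT-group patients whose tested blastocyst is euploid lies between 50% (illustrative) and a ceiling. The ceiling holds if the rates come from comparable patients: the morphology rate is then *e* × euploid rate plus a contribution from aneuploid embryos that cannot be negative, so *e* ≤ 0.52/euploid rate. That is 0.52/0.72 = 72% for a 72% euploid rate and 0.52/0.66 = 79% for 66%.

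**Formula.** Power = Φ[(d − z·se₀)/se₁], where se₀ = √(p̄(1−p̄)·2/n), se₁ = √((p₁(1−p₁)+p₂(1−p₂))/n), and z = 1.645 one-sided or 1.960 two-sided.

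**Step 1: reproduce 74.** For 52% v 72% the same formula solved for n gives 72 per group one-sided and 92 two-sided. For 46% v 66% it gives 76 and 96. For the quoted 52% v 66% it gives 152 and 193. So, on the quoted rates, 74 is recovered only as a per-group, one-sided, 20-point figure with no dilution. At n = 74 and 52% v 72%, se₀ = 0.0798 and se₁ = 0.0781:
- one-sided: Φ[(0.20 − 0.1313)/0.0781] = 81%
- two-sided: Φ[(0.20 − 0.1564)/0.0781] = 71%

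**Step 2: 20 points as the euploid-transfer effect.** PGT-group rate = *e* × 0.72 + (1 − *e*) × 0.52, with 74 per arm:

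| *e* | PGT-group rate | Difference from 52% | Two-sided power | One-sided power |
|---|---|---|---|---|
| 100% (no dilution) | 72.0% | 20.0 points | 71% | 81% |
| 72% | 66.4% | 14.4 | 43% | 56% |
| 70% | 66.0% | 14.0 | 41% | 53% |
| 60% | 64.0% | 12.0 | 31% | 43% |
| 50% | 62.0% | 10.0 | 23% | 34% |

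In the two-sided column, the fall from 80% to 71% is due to sidedness; only the further fall is dilution. For 80% power, *e* = 72% would need 181 per arm two-sided (143 one-sided), and *e* = 50% would need 384 (303).

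Sensitivity to the next-best rate, *e* = 50-72%: at 45%, power is 12-34% two-sided; at 59%, it is 38-53%.

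**Step 3: 20 points as the between-arm difference.** Nothing is left to dilute, so 74 per arm gives 81% one-sided or 71% two-sided. But *e* × (euploid rate − 0.52) must then equal 0.20, so the euploid rate must be 0.52 + 0.20/*e*:
- *e* = 79%: 77%
- *e* = 50%: 92%

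The centre's own figure is 66%. The 77% is generous, because a 77% euploid rate would itself lower the ceiling on *e* to 0.52/0.77 = 68%.

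**Step 4: 74 as the number of euploid patients.** The PGT group must randomise 74/*e*: about 94 at *e* = 79% and 148 at *e* = 50%. No such number is stated.

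**The case against.** The strongest reply is that the plan never says the 20 points is the euploid-transfer effect. Read as the detectable difference between randomised groups, 74 per arm does give about 80% power one-sided, and dilution costs nothing. That reply stands as far as it goes. A reader might infer that 74 fails to deliver 80% power on any reading, and the documents do not support that. What remains on this reading is the implausibility shown in Step 3: an effect well beyond the centre's own euploid rate.

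A reader might also infer that the objectives contradict each other. They do not quite. The Introduction poses the same selection-method question as Objectives and then describes it through transfer types, while Objectives names no analysis groups. The supportable statement is that the comparison is unclear.

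The euploid fraction is not in the documents, and the 50% lower limit is illustrative, so the exact power figures are conditional. The direction does not depend on it: whenever *e* is below 100% and next-best transfers do less well than euploid ones, the PGT group falls short of the euploid rate.

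The protocol already defines the euploid and aneuploid groups as subgroups in advance. That helps, but it does not say which contrast is primary. The gap between the centre's 14 points (66% − 52%) and the planned 20 is a separate discrepancy and is not counted here.

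**Conclusion.** The concern holds as an omission and an ambiguity. The sample size takes its rates from euploid v morphology transfers, allows nothing for untested transfers within the PGT group, and leaves the comparison, the unit of 74 and the sidedness unstated. Confidence in this is high, because it rests on the text.

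The size depends on the reading:
- **Euploid-transfer effect, 74 per arm:** the randomised comparison falls from 81% to about 34-56% power one-sided, or from 71% to about 23-43% two-sided, under the assumptions listed (next-best at 52%, *e* = 50-72%).
- **Between-arm difference:** the power is about as stated if the test is one-sided, but the effect requires a euploid rate of at least about 77% (next-best at 52%, *e* no more than 79%).
- **Euploid patients:** the required PGT group of about 94-148 is missing, and the comparison is not between randomised groups.

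This should be corrected. It limits what a result may claim; it does not show that the trial's design is invalid.

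**What to change.** 1. In the Sample size calculation, name PGT group v morphology group, as randomised, as the primary comparison. Label euploid subgroup v morphology group as secondary and non-randomised.
2. In the same section, restate the power at n = 74 with the PGT-group rate written as *e* × euploid rate + (1 − *e*) × next-best rate, over a stated range of *e* or the centre's own fraction. State the sidedness and what 74 counts.
3. In the Introduction and Secondary objectives, word the objectives, and the conclusions drawn from them, for the strategy tested: PGT of the single best blastocyst, with the untested next-best one transferred if it is aneuploid. Mark any claim about euploid transfer as non-randomised.

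The cost is one recalculation, some wording and a less favourable stated power. No patients or procedures are added, so 80% power is not restored. The registration-changes section gives an analysis start of 25 April 2018, so the practical gain is in how results are read; any restatement should carry its own date.

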## Interventions

### Controlled ovarian stimulation, oocyte pickup, and embryo culture

All patients will have an ultrasound examination on cycle day 2 or 3 to assess the state of the patients ovaries and uterus, and perform an antral follicle count (follicles  $>2 \leq 10$  mm), before commencing flexible start gonadotropin-releasing (GnRH) antagonist (0.25mg, Cetrotide, Merck Serono, Istanbul, Turkey) co-treatment OS protocols. Follicular development will be stimulated using a combination of rFSH (150-375 IU, Gonal-F, Merck Serono, Istanbul, Turkey) and hMG (75-150 IU, Menopur, Ferring Pharmaceuticals, Mumbai, India). The gonadotropin doses will be based on maternal age, BMI, AFC, and previous OS outcome. Final oocyte maturation will be triggered when three or more follicles reach  $\geq 17$  mm, with GnRHa (0.2 mg, Gonapeptyl®, Ferring Pharmaceuticals, India).

Oocyte retrievals will be performed 36 hours after triggering using transvaginal ultrasound (TVS) guided follicle aspiration (follicular aspiration needle, 461230LF, Rheinbach, Germany) procedures. Oocyte collection and manipulation will be performed using Cook Medical media (Sydney IVF, Brisbane, Australia) and embryo culture will be performed using SAGE 1-Step™ medium (67010010A, SAGE, Origio, Malov, Denmark), with no change of media during culture. Incubation conditions were set at 6% CO2, 5% O2 and 37.0°C (G185 Long Term Flat Bed Incubators, K-Systems, Kivex Biotec ltd, Birkerod, Denmark). All oocyte inseminations will be performed using ICSI, with daily embryo development assessments, thereafter.

### Blastocyst assessment

Blastocysts will be graded according to the 3-part grading system (Gardner *et al.*, 2000), with a blastocyst grade including an assessment of blastocyst expansion (grade 1 to 6), inner cell mass morphology (ICM, A to C, according to the number and degree of compaction of the cells), and trophectoderm morphology (TE, A to C, according to the number, size and contiguous arrangement of the trophectoderm cells). Blastocysts with a grade of  $\geq 2BB$  were regarded as usable.

## **Biopsy**

Blastocysts with morphological grades of  $\geq 2$ BB will be biopsied on day 5 of in vitro embryo culture. Biopsies will be performed using a Hamilton Thorne Zilos laser (Hamilton Thorne, MA, USA), with 3-10 trophectoderm cells removed from the blastocysts.

## **Comprehensive chromosome screening**

All trophectoderm biopsies will be processed for analysis by Next-Generation Sequencing (NGS, illumina, California, USA).

## **Blastocyst cryopreservation**

Vitrification and warming of blastocysts will be performed using ultra-rapid technologies (Cryotop, Kitazato BioPharma Co. Ltd, Fuji-city, Japan), according to the manufacturer's guidelines. Blastocysts were warmed and transferred on the same day; after warming the blastocysts were placed in incubation for approximately 2 hours and then morphologically reassessed.

## **Cycle programming and endometrial preparation**

All patients will undergo a standard endometrial preparation protocol, using GnRHa to programme the start of the endometrial preparation (Ozgur *et al.*, 2016).

## **Frozen embryo transfer art-FET**

All transfers will be SET and performed in art-FET. Embryo transfers will be performed with glass syringes (50 $\mu$ L, Hamilton, Giarmata, Romania) attached to embryo replacement catheters (Wallace, Smiths Medical, Kent, UK), with trans-abdominal ultrasound guidance. All blastocyst FET will be scheduled to be performed on the 6th day of progesterone administration (90 mg, twice-a-day, Crinone®, Merck Serono, Turkey) to time the day of transfer, with progesterone administration commencing on day 15 of endometrial preparation.

